**BRACHY-CHOR-001** 

A separate table to summarize time to worsening in BPI-SF "Worst" pain item by best overall response will also be presented. A worsening in "Worst" pain item is defined as an increase in post-baseline pain score of at least 2 points and worsening in pain category among subjects who had no or mild pain at baseline and moderate or severe pain post-baseline or moderate pain at baseline and severe pain post-baseline. Time to worsening is defined the number of weeks in subjects who had at least a 2 point increase in pain and with no or mild pain at baseline to moderate or severe pain post-baseline or with moderate pain at baseline to moderate or severe pain post-baseline (Cleeland, 2013). A Kaplan Meier figure will be provided for the time to worsening in the subset of subjects who experience pain worsening and the figure will be plotted by best overall response.

To further explore the correlation between pain score and tumor response, worst observed BPI-SF scores by period and best observed BPI-SF scores will be summarized for subjects with any shrinkage in irradiated target lesions throughout the trial. Shrinkage in irradiated target lesions is defined as measurable lesions irradiated as part of trial treatment which decreased in length after baseline. Subjects are counted in the "Any shrinkage" category based on a decrease in the sum of the longest diameter of the irradiated target lesions of least a 5 mm. If there is no change, a decrease of less than 5 mm in the sum of the longest diameter of the irradiated target lesions or an increase in the sum of the longest diameter of the irradiated target lesions, subjects are counted in the "No shrinkage" category.

Shift tables of BPI-SF scores from baseline to worst observed values within each post-baseline periods and worst observed values in overall treatment period, and from baseline to best observed values within each post-baseline periods and best observed values in overall treatment period will also be presented by pain score categories for each BPI-SF item.

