#### **Secondary efficacy endpoints:**

- PFS by mRECIST 1.1 or irRC on target lesion(s)
- Improvement in clinical symptoms measured by the BPI-SF

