## 3.5.3.4 Secondary Efficacy Analyses

## 3.5.3.4.1 PFS Based on Target Lesion(s)

PFS is defined as the time interval from first vaccination to objective tumor progression based on the mRECIST criteria or death, whichever occurs first. Subjects who do not have disease progression or have not died will be censored at the date when the last tumor assessment determines a lack of target tumor progression. The product-limit Kaplan-Meier curve will summarize PFS graphically. Median survival and 95% confidence intervals will be computed based on the product limit method (Greenwood's formula for the standard error estimate) overall and by subgroups defined in Section 3.3. Progression-free survival rates will be summarized by visit where scheduled tumor assessment is performed, along with their Wilson score confidence intervals.

Primary analyses of PFS will be based on the EAS. PFS rates will also be summarized for the FAS where subjects without post-treatment tumor assessment will be considered to have progressed. Median survival and 95% confidence interval will not be analyzed for the FAS, as these estimates will not differ from those for the EAS because censoring at time 0 is equivalent to excluding these subjects.

Additionally, PFS from current treatment versus PFS from previous treatment will be explored. The ratio of current treatment PFS in days / previous treatment PFS in days for each subject will be calculated. Summary statistics will be presented for EAS. It will also be summarized for EAS by current radiation treatment dose categories: <= median current radiation dose in Gray and > median current radiation dose in Gray. Highest dose of radiation treatment for each subject is used as defining the current radiation treatment dose categories. Subject's most recent previous treatment will be used for the derivation and calculation of PFS from previous treatment. Figures will also be generated to present the ratio by overall and by current treatment radiation dose categories.

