#### 3.5.3.4.2 **BPI-SF**

The following pain intensity and pain interference scores (Cleeland, 2009) will be summarized and listed:

- From the eCRF, pain intensity recorded as "Worst", "Least", and "Average" in the last week and pain intensity recorded as "Right now".
- Composite pain severity score (a mean severity score of the above four pain items)

BRACHY-CHOR-001

- Composite pain interference score (a mean of the seven interference items). This will be calculated if at least four of the seven interference items have been completed on a given administration. Otherwise, the pain interference score will be considered missing.

For each subject, the worst observed score and the best observed score during the following periods will be summarized:

- Pre-Radiation Vaccination Period
- Radiation Therapy Period
- Post-Radiation Vaccination Period 1
- Post-Radiation Vaccination Period 2
- Overall Treatment Period

A score of 10 is the worst pain imaginable and a score of 0 is no pain. The worst score in each period is defined as the highest value within the period. The best score in each period is defined as the lowest value within the period.

Pain score category is defined for the "Worst" pain endpoint as 0 as no pain, 1-4 as mild pain, 5-6 as moderate pain and 7-10 as severe pain (Serlin, 1995).

For summary tables, the primary analysis will be performed on the EAS with additional analyses performed on the FAS. Continuous summary statistics will be provided for the worst observed score and the best observed score within each period for "Worst", "Least", "Average", and "Right Now" pain intensities as well as composite pain severity and composite pain interference scores. Individual pain interference items will be included in subject-level listings and will be plotted.

To explore if there is a correlation between tumor response and pain score, continuous summary statistics will be provided for the worst score within each period for "Worst", "Least", "Average", and "Right now" pain intensities as well as composite pain severity and composite pain interference scores by best overall tumor response per mRECIST. Similarly, a summary table will be provided for the best score within each period by best overall tumor response. Mean score and 95% CI will also be plotted over time by visit and by best overall tumor response for each BPI-SF item.

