Additionally, a separate table will be presented for the number of subjects with improvement in "Worst" pain item and continuous summary statistics of the duration of improvement by best overall tumor response. Improvement in "Worst" pain item score is defined as a subject that has a reduction in pain score of 2 points from baseline and remains a reduction in pain score for at least 1 timepoint after the initial timepoint with pain reduction post-baseline (Cleeland, 2013). The duration of improvement is defined as the difference in weeks between the first timepoint of reduction in pain score of 2 points from baseline to the timepoint before an increase in pain of at least 2 points from the nadir value during the improvement time period. A Kaplan Meier figure will be provided for duration of improvement in the subset of subjects who experience pain improvement. The plot will be stratified by best overall response.

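### The Kaplan-Meier figure for time to pain worsening includes only subjects who worsened, so every curve must fall to zero and it cannot compare worsening by tumor response

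*SAP*

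**What the plan says.** SAP 3.5.3.4.2 (BPI-SF) plans a table and a Kaplan-Meier figure of time to worsening in the Worst pain item.

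- **Event:** "an increase in post-baseline pain score of at least 2 points and worsening in pain category". The qualifying moves are from no or mild pain to moderate or severe, and from moderate to severe.
- **Pain categories:** "0 as no pain, 1-4 as mild pain, 5-6 as moderate pain and 7-10 as severe pain".
- **Time variable:** "Time to worsening is defined the number of weeks in subjects who had at least a 2 point increase in pain", followed by the category conditions.
- **Figure:** "A Kaplan Meier figure will be provided for the time to worsening in the subset of subjects who experience pain worsening". Separate curves are drawn for each category of best tumor response.

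Neither document gives a time value or a censoring date for subjects who do not worsen. The SAP does give such a rule for PFS. In section 3.5.3.4.1, subjects without progression or death "will be censored at the date when the last tumor assessment determines a lack of target tumor progression".

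The BPI-SF supports one of the two secondary efficacy endpoints in SAP 1.5: "Improvement in clinical symptoms measured by the BPI-SF".

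**The concern.** The subset is selected on the very event being timed. Every subject with baseline pain below the severe category is at risk of worsening from baseline. Those who never worsen carry the information about how rare worsening is. Once they are removed, nobody is censored and the estimate is just the distribution of event times among subjects with events.

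The figure is meant to show whether pain worsening differs by tumor response. As specified, it shows 100% worsening in every plotted group, however few subjects worsened, and it understates time to worsening. Two groups whose risks differ several-fold can give similar curves. A response group with no worsening, the best possible result, drops off the plot.

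**Working it through.** The plan states no figure for this analysis, so there is nothing to reproduce. The check has four steps.

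**1. The fall to zero needs no assumption.** The product-limit estimate is S(t) = Π(1 − dᵢ/nᵢ) over event times up to t. If every subject in the set has the event, those still at risk at the last event time all have it then. So d = n, the last factor is 0, and S = 0.

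**2. Size under an assumed model.** The risks and the exponential form are assumptions, because the documents give none. For worsening risk F by horizon L:

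- hazard λ = −ln(1 − F)/L
- median in all subjects = ln 2/λ
- median among worseners only solves F(t) = F/2, so t = −ln(1 − F/2)/λ

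With L = 110 weeks (the last scheduled vaccination visit after radiation):

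- F = 0.20: λ = 0.2231/110 = 0.00203; worsener-only median 0.1054/0.00203 = 51.9 weeks; true median 0.6931/0.00203 ≈ 342 weeks.
- F = 0.60: λ = 0.9163/110 = 0.00833; worsener-only median 0.3567/0.00833 = 42.8 weeks; true median 0.6931/0.00833 ≈ 83 weeks.
- Hazard ratio = 0.9163/0.2231 = 4.1.

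The 110 weeks in the schedule run from the end of radiation, while worsening is judged against baseline. Radiotherapy is placed at about Day 42 to 70 (weeks 6 to 10), so an assumed 118-week horizon was also run, with other risks.

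| L (weeks) | Assumed risks | Free of worsening at L, all subjects | Same, worseners only | Worsener-only medians (weeks) |
|---|---|---|---|---|
| 110 | 20% / 60% | 80% / 40% | 0% / 0% | 51.9 / 42.8 |
| 118 | 20% / 60% | 80% / 40% | 0% / 0% | 55.7 / 45.9 |
| 118 | 10% / 60% | 90% / 40% | 0% / 0% | 57.4 / 45.9 |
| 118 | 30% / 30% | 70% / 70% | 0% / 0% | 53.8 / 53.8 |

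At 118 weeks the true median for the 20% group is 0.6931 × 118/0.2231 ≈ 367 weeks.

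**3. The order of the groups can reverse.** Take 29 subjects, the planned number, with invented data. Of 10 responders, 1 worsens, at week 10. Of 19 non-responders, 12 worsen, at weeks 6, 10, 14, 20, 26, 26, 38, 38, 50, 50, 62 and 74. All others are event-free to week 110.

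- As the SAP is written: the responder curve has n = 1 and is 0 at week 10. The non-responder curve has n = 12, a median of 26 weeks (6 of 12 events by then) and is 0 at week 74. Responders look worse.
- With all subjects and censoring: S at week 110 is 9/10 = 0.90 in responders and 7/19 = 0.37 in non-responders.

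**4. Who is at risk.** Severe (7 to 10) is the top category, so a subject who starts there cannot move to a worse one. The at-risk set is therefore baseline 0 to 6. The time-to-worsening sentence also lets moderate pain go to moderate or severe, whereas the event definition requires severe. On integer scores the two agree, because a rise of 2 from 5 or 6 gives at least 7.

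**The case against.** The case on the other side is mainly about weight. The listed endpoint is improvement in symptoms; worsening is not named. Protocol 10.4.5.2 plans only continuous BPI-SF summaries by study period. The SAP frames its pain-by-response analyses as exploratory, no test depends on the figure, and about 29 subjects split by response would give sparse curves in any form. The subset is openly labelled, so the curves can still be read as timing among worseners. This stands and limits the importance of the point.

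Other displays do keep non-worseners: worst scores per period and mean scores by visit, both by response, and baseline-to-worst shift tables. None gives time to worsening or its incidence by response. The shift tables are by pain category and are not specified by response. A count of improvers is planned, but no matching count of worseners. Mock tables are in a separate document, so counts may appear there.

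The restriction could be read as applying to the figure alone, with the time-variable sentence a clumsy event definition. Even so, the table has no stated rule for subjects without the event.

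The SAP uses similar wording elsewhere: "A Kaplan Meier figure will be provided for duration of improvement in the subset of subjects who experience pain improvement". That restriction is legitimate, because duration begins only once improvement has occurred and ends with its loss. Time to worsening runs from baseline for everyone.

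Finally, the correction leaves two limits. Best response is known only from about 14 weeks after radiation, so grouping by it carries immortal-time bias. Censoring at the last BPI-SF may also be informative when progression leads to discontinuation. Both deserve a note, but neither justifies dropping the event-free subjects.

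**Conclusion.** The concern holds. As written, every plotted curve reaches zero by construction, so the figure cannot show the risk of, or the time to, pain worsening by tumor response. It shows only the timing among those who worsened. That conclusion rests on the SAP wording and the form of the estimator alone. The sizes rest on assumed risks and exponential times; moving the horizon from 110 to 118 weeks changes nothing material.

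The consequence is confined to a descriptive analysis within a secondary endpoint. The response-rate decision and PFS are unaffected. It should still be corrected before the analysis is run. The SAP Introduction commits to following the plan completely and to labelling anything extra as unplanned, so a valid version added later would carry that label.

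**What to change.** Amend SAP 3.5.3.4.2 as follows:

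- **Population:** all EAS subjects with a baseline Worst score of 0 to 6, with the FAS as the additional analysis. State that severe baseline pain is excluded because the category condition cannot be met, and how many subjects this removes.
- **Time and event:** weeks from baseline to the first visit meeting the worsening rule. Name the time origin explicitly.
- **Censoring:** subjects without the event are censored at their last BPI-SF assessment. State how death is handled.
- **Display:** run both the table and the Kaplan-Meier figure on this set, with numbers at risk and the number worsening in each response group.
- **Interpretation:** note that grouping is by a post-baseline outcome. A landmark or time-dependent analysis would address the resulting bias.
- **Tidying:** use one wording for the moderate-baseline condition. This changes no result.

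The cost is SAP text and a changed input data set for one table and one figure. The BPI-SF is scheduled from Day 0 at every later visit, so the censoring dates need no new data.

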## 2.3 Role of Radiotherapy in Treatment of Chordoma

Radiotherapy is a core treatment modality for the management of chordoma. Radiotherapy appears to play a critical role in the local recurrence rate after surgical resection (DeLaney et al., 2009, Chen et al., 2013, Park et al., 2006). Despite the apparent ability of high dose radiation to prevent recurrence in historical (uncontrolled) case series, the effects on established chordoma tumors is less readily measured. In fact, an analysis of chordoma cases treated with high dose radiotherapy found less than 5% of all patients had objective responses by RECIST (>30% decrease in sum of single axes). At 12 months, none of the patients had achieved objective response. Only at about 18 months had any patients reached the 30% tumor size reduction required for a response, and those were still a small minority of cases (<5%) (Kabolizadeh et al., 2017). Based on these findings, it appears we can confidently state that the expected historical response rate with radiotherapy alone in chordoma is 0-5% at 1 year.

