## **Measurable Disease**

Measurable lesions are defined as those that can be accurately measured in at least one dimension (longest diameter to be recorded) as > 20 mm by chest x-ray, as > 10 mm by CT scan, or > 10 mm with calipers by clinical exam. All tumor measurements must be recorded in millimeters (or decimal fractions of centimeters).

Note: Tumor lesions that are situated in a previously irradiated area might or might not be considered measurable.

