## 3.5.3.2 Response Criteria

### **Primary and Secondary Endpoints**

mRECIST criteria will be used for radiographic assessment of the irradiated tumor(s) (target lesions) only. Non-irradiated tumors (non-target lesions) will not be assessed for the primary endpoint by mRECIST, but clinical decisions based on tumor growth may be made on investigator discretion. Additionally, at investigator discretion, irRC principles can be used for target lesion(s). If a subject has enlargement of their target lesion(s) at the first restaging scan after completion of radiotherapy, they may remain on trial until confirmation of progression on a subsequent scan (at least 4 weeks later). Similarly, any response must also be confirmed with a repeat scan at least 4 weeks later. Progression of a non-target lesion does not result in disease progression by the mRECIST evaluation to be used in this trial. The purpose of the trial is to determine if radiation plus vaccine can shrink the irradiated tumor. In these cases, local interventions may be considered to other non-target lesions (surgery, radiation, or ablation) at the investigator's discretion. Progression of any non-target lesion that requires systemic treatment will result in the subject being taken off trial. If a subject must come off trial due to progression of any non-target lesion prior to meeting the evaluable definition, they may be replaced with another subject to ensure statistical power is maintained for the primary analysis.

In some cases, if more than one lesion can be irradiated, multiple target lesions may be selected. Only those that receive adequate radiotherapy (as defined by radiation requirements for enrollment in the trial protocol) will be considered target lesions for RECIST assessments and primary endpoint analysis.

BRACHY-CHOR-001

All subjects in this trial must be assessed for response to treatment, even if there are major treatment deviations. If a subject has not completed adequate treatment to be evaluated for response to treatment, they should still be assessed, but may be replaced to maintain statistical power. The primary endpoint assessment of ORR anytime within 12 months following completion of radiation will be based on the response to adequate treatment, which will require vaccination and completion of adequate radiotherapy. Progression prior to that point will not be considered treatment failure for purposes of primary endpoint analysis.

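### SAP 3.5.3.4.2: the unconfirmed 5 mm 'Any shrinkage' rule picks up chance falls that accumulate with the number of scans, and can place a small-lesion partial responder under 'No shrinkage'

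*SAP*

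**What the plan says.** SAP 3.5.3.4.2 (BPI-SF) adds a pain summary split by tumor shrinkage. Worst and best observed pain scores will be "summarized for subjects with any shrinkage in irradiated target lesions throughout the trial". The paragraph defines shrinkage twice. It first describes "measurable lesions irradiated as part of trial treatment which decreased in length after baseline", with no threshold. It then sets the working cut: "Subjects are counted in the 'Any shrinkage' category based on a decrease in the sum of the longest diameter of the irradiated target lesions of" at least 5 mm. A smaller fall, no change or an increase all go to 'No shrinkage'. The paragraph does not say which scan decides and does not mention confirmation.

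The SAP is stricter elsewhere. Under SAP 3.5.3.2, "any response must also be confirmed with a repeat scan at least 4 weeks later". Within 3.5.3.4.2 itself, improvement in worst pain must persist for at least one further timepoint.

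On lesion size, Protocol 2.3 gives the response threshold as a relative one, "objective responses by RECIST (>30% decrease in sum of single axes"). Protocol Appendix 1 admits lesions as measurable from "as > 10 mm by CT scan".

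**The concern.** The rule compares one baseline sum with every later sum and needs only one qualifying difference. Each extra scan gives measurement error another chance to produce a 5 mm fall. The number of chances differs widely between subjects: the evaluable set requires one post-baseline scan, while a subject who completes the schedule has up to ten. Because target-lesion progression ends vaccination (Protocol 4.2.5), length of follow-up is itself related to outcome.

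The cut is also absolute while response is relative, so for a small baseline sum the two can disagree about the same subject. That subject would sit with the responders in the table by best overall response and under 'No shrinkage' in the next table.

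What is at stake is how this one table is read. Standard RECIST, Choi and volumetric analyses have been dropped (SAP 3.5.3.5). The shrinkage split is therefore the main remaining pain comparison that uses tumor change smaller than a formal response.

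**Working it through.** **Plan's own figures.** The documents give no error rate for this rule and no measurement SD. Their only design figures are those of the Simon design. These reproduce (type I error 0.047, power 0.801, early stopping 0.599, expected size 17.6 under 5%) but do not bear on this point.

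**Inputs.**
- Threshold: 5 mm on the sum (SAP 3.5.3.4.2).
- Post-baseline scans: weeks 14, 26, 38, 50, 62, 74, 86, 98 and 110 after radiation, which is 9, plus the 30-day follow-up scan, which makes 10 (Protocol 1.5; SAP Appendix 1). Four of these fall by week 50.
- Assumed: s, the SD of a single measurement of the target sum, ranged over 2 to 5 mm; independent normal errors; no true change in size.

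**Chance label, k scans.** All k comparisons share the baseline error e, so

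P = ∫ φ(e; 0, s) × [1 − (1 − Φ((e − 5)/s))^k] de.

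For k = 1 this is Φ(−5/(s√2)). At s = 2 that is Φ(−1.77) = 0.039, and at s = 5 it is Φ(−0.71) = 0.24.

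| s (mm) | 1 scan | 2 scans | 4 scans | 10 scans | 10 scans, two consecutive |
|---|---|---|---|---|---|
| 2 | 4% | 7% | 12% | 20% | 4% |
| 3 | 12% | 20% | 30% | 45% | 16% |
| 4 | 19% | 30% | 43% | 60% | 27% |
| 5 | 24% | 37% | 51% | 68% | 34% |

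The last column is a simulation of 400,000 subjects per row in which the 5 mm fall must appear on two consecutive scans. At s = 1 mm the 10-scan rate is 0.2%.

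**Correlated errors.** If all errors, baseline included, have correlation 0.5, s is replaced by s√(1 − 0.5). For s = 4 that is 2.83 mm, and the 10-scan rate falls from 60% to 42%.

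**Dependence on follow-up.** Take s = 4 and stable subjects of whom half have 2 scans (29.7% labelled) and half have 10 (59.5%). The 10-scan subjects make up 59.5/(29.7 + 59.5) = 67% of 'Any shrinkage', and 40.5/(70.3 + 40.5) = 37% of 'No shrinkage'. The pain outcomes are the highest and lowest scores in a period. In the overall treatment period and in Post-Radiation Vaccination Period 2, these extremes also widen with the number of visits.

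**Dilution.** The share of a true pain difference that survives misclassification is PPV + NPV − 1. With sensitivity 0.95 and a 50% false-positive rate:
- 30% truly shrinking: 0.285/(0.285 + 0.35) + 0.35/(0.35 + 0.015) − 1 = 0.41.
- 70% truly shrinking: 0.665/(0.665 + 0.15) + 0.15/(0.15 + 0.035) − 1 = 0.63.

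With a 20% false-positive rate the range is 0.64 to 0.79.

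**Conflict with partial response.** A 30% fall is less than 5 mm when the baseline sum is below 5/0.30 = 16.7 mm. In whole millimeters, a 30% fall needs 4 mm for sums of 11, 12 and 13 mm (3.3, 3.6 and 3.9 rounded up) and already needs 5 mm at 14, 15 and 16 mm (4.2, 4.5 and 4.8 rounded up). Two measurable lesions sum to more than 20 mm, so the conflict arises only with a single small target lesion.

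**The case against.** The strongest reply is that this is a deliberately loose, descriptive split. The SAP says it is there to explore further a correlation, and attaches no test or decision to it. Pain is also tabulated and plotted by best overall response, where confirmation applies and a partial response counts as one. Percent change in the target lesion is plotted by visit, and measurements are listed. The secondary endpoint is improvement on the BPI-SF, and its definition does not use the shrinkage flag. All of this stands, and it keeps the point minor.

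Three stronger readings are tempting, but the documents do not support them.

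- **More than half of stable patients would be mislabelled.** That needs an SD of about 3.3 mm or more, independent errors and all ten scans. The documents give no SD, and Protocol 9.4 asks each site to keep the same equipment and scanning parameters, so independence may be too pessimistic. With one scan the rate cannot exceed 50% at any SD.
- **The comparison does not discriminate.** A true 10 mm fall is flagged in at least 99% of subjects over nine scans at SD 2 to 4 mm, and 41 to 63% of a true pain difference survives even a 50% false-positive rate. The effect is dilution plus dependence on follow-up.
- **Every sum between 10 and 16.7 mm contradicts partial response.** The conflict needs a fall of at least 30% that never reaches 5 mm at any scan. The documents give no lesion-size distribution, so its frequency is unknown.

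The reply leaves two things unanswered. The SAP asks for persistence for tumor response and for pain improvement but not here, and two adjacent tables can classify the same responder in opposite ways.

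**Conclusion.** The point holds as a minor one. As written, the rule gives a truly stable tumor a 4 to 24% chance of the 'Any shrinkage' label with one scan and 20 to 68% with ten. This assumes independent normal errors with SD 2 to 5 mm on the sum, and the rates are lower if errors are correlated. The exploratory comparison is weakened and partly reflects how long subjects were followed.

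The conflict with partial response needs no assumption about error, but it is a corner case confined to a single target lesion below 16.7 mm. A reader might infer that the pain endpoint or the trial's conclusion is compromised. It is not: the primary endpoint and the BPI-SF improvement definition do not depend on this flag.

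**What to change.** In SAP 3.5.3.4.2, replace both shrinkage sentences with one rule. A subject counts as 'Any shrinkage' if the target sum falls at least 5 mm below baseline and the fall is confirmed on the next scan at least 4 weeks later, or if best overall response is CR or PR. Let the 30-day follow-up scan confirm a fall first seen at the last dose visit. The visit window of 30 ± 2 days puts it 28 to 32 days later, which meets 4 weeks if the earlier scan was taken by that visit. Keep the window as the whole trial, and show the unconfirmed single-scan split as a sensitivity table.

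The confirming scan should be the next one. If any later scan could confirm, the same integral with at least two of ten scans qualifying gives 9%, 27%, 41% and 50% at SD 2, 3, 4 and 5 mm, against 4%, 16%, 27% and 34% for consecutive scans. Confirmation reduces chance labels but does not remove them.

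Two further changes are not recommended. A percentage threshold would be a preference with no source in the documents. A 12-month limit would discard late shrinkage: Protocol 2.3 reports that with radiotherapy alone, 30% reductions first appeared at about 18 months.

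The cost is SAP wording and one derived flag, using scans already scheduled. The shrinkage group becomes smaller, and a fall seen only on the final scan is not counted unless the subject is a CR or PR.
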